2. OBJECTIVES

The primary objective of the study is to identify risk factors for cancer onset in the population affected by T2D.

Secondary objectives include:

1. Description of demographic, clinical, and first-line therapy characteristics of patients at the diagnosis of T2D.
2. Evaluation of risk factors for recurrence, presence of a second cancer unrelated to the first, and presence of both events in patients who have had cancer.
3. Investigating the correlation between patient characteristics and time to cancer onset.

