3.3 Subjects

All patients visited at the Endocrinology and Diabetology Outpatient Clinic of the AOU Maggiore della Carità in Novara for a first diagnosis of T2D between 1990 and 2010 will be included in the study.

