3.6 Follow-up and Events of Interest

Patients included in the study will be followed from the date of diagnosis of T2D until the date of the last available visit.

During the follow-up, for all included patients, the year of onset of the first cancer occurring after the diagnosis of diabetes and the type of cancer will be recorded. From this information, it will be possible to calculate the time elapsed between the diagnosis of diabetes and the onset of the tumor (measured in years).

For patients who have developed cancer, the following will also be recorded:

- Cancer recurrence (year of recurrence onset)
- Diagnosis of a second cancer unrelated to the primary cancer (year of onset, type of cancer)

Cancer diagnosis will be identified through the extraction system from the Smart Digital Clinic electronic medical record (Meteda Srl), using relevant keywords in the cancer domain, identified in the medical history section. The keywords will include: metastasis, adenocarcinoma, carcinoma, neoplasm, secondary, sarcoma, cancer, adenoma, lymphoma, leukemia, glioma, glioblastoma, basal cell carcinoma, squamous cell carcinoma, melanoma, mesothelioma, chordoma, anaplastic, differentiated, undifferentiated, meningioma, multiple myeloma, small cell carcinoma, thymoma, craniopharyngioma, neuroendocrine, LH, NHL, K, GIST, HCC, and NET.

SCDU di Endocrinologia

AOU Maggiore della Carità, [name]
[contact] (Reparto); [contact]
[contact]

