3.7 Data Collection

For each patient, the following variables will be extracted from the Smart Digital Clinic electronic medical record extraction system, when possible:

- Gender and age;
- Smoking habit and alcohol consumption (units per day);
- Weight and body mass index (BMI) at the first (T0) and last visit (T1);
- Date of diagnosis of T2D;
- Date of the first visit;
- Treatment for T2D at T0 and T1;
- Levels of glycated hemoglobin (HbA1c) at T0 and T1, average HbA1c, and average fasting blood glucose;
- Creatinine clearance at T0 and T1;
- Liver enzymes at T0 and T1: alanine aminotransferase (ALT) and aspartate aminotransferase (AST);
- Lipid profile at T0 and T1: low-density lipoprotein (LDL-c) and triglycerides (TG);
- Complications of T2D;
- Treatment for the cancer;
- Family history of cancers.

The diagnosis of T2D is confirmed at diabetic centers or, in some cases, by general practitioners who refer patients to specialized diabetic centers. The accuracy of the diagnosis will be confirmed by cross-referencing with the Piedmont Diabetic Registry (PDR) and involving a second person to ensure precise assessment.

Glycated hemoglobin will be considered high if its values exceed or equal 8%, indicating glycemic decompensation, while it will be considered low if it presents values below 8%.

BMI categories will be divided into underweight (BMI <18.5 kg/m²), normal weight (BMI 18.5 – 25 kg/m²), and overweight (BMI >25 kg/m²).

Regarding the treatment of T2D, participants will be categorized and grouped for statistical purposes into the following classes:

- Dietary therapy;
- Metformin/Acarbose;
- Sulfonylurea;
- Metformin + GLP1/DPP4 inhibitors (DPP4i) or only GLP1 or only DPP4i;
- Metformin + SGLT2 inhibitors (SGLT2i) or only SGLT2i;
- Basal insulin + GLP1/DPP4i +/- Metformin;
- Basal insulin +/- Metformin +/- SGLT2i;
- Basal bolus insulin;
- Basal bolus insulin +/- Metformin +/- SGLT2i.

Furthermore, complications of metabolic pathology will be extracted from the dedicated section of the program, where they are systematically recorded and organized, and their diagnosis is conducted in accordance with appropriate guidelines. These complications will be divided into the following categories: vasculopathy, neuropathy, hypertension, heart disease, renal failure, and retinopathy.

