3.8 Sample Size

Assuming a type I error of 0.05, a power of 80%, a prevalence of subjects with high glycated hemoglobin levels of 13%, and a correlation between covariates in the model of 0.1, it will be necessary to identify 779 cancer cases to highlight a Hazard ratio of 1.2 for the association between glycated hemoglobin and cancer onset.

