3.9 Statistical Analysis

Descriptive statistics will be calculated to summarize patient information.

Categorical variables will be reported as absolute frequencies and percentages, while numerical variables will be reported as mean and standard deviation or median (Q1-Q3) if not distributed according to a normal random variable according to the Shapiro-Wilk test and observation of the QQ plot.

SCDU di Endocrinologia

AOU Maggiore della Carità, [name]
[contact] (Reparto); [contact]
[contact]

Univariate and multivariate Cox proportional hazards regression models will be used to estimate hazard ratios (HRs) and corresponding 95% confidence intervals (95% CI) for the association between some risk factors, including particularly glycemic level, and cancer onset. The stepwise method will be used to select variables to include in the model. For this analysis, time to event will be calculated as the number of years between cancer onset and diabetes diagnosis for subjects who develop the cancer, and as the number of years between the last available visit and the date of diabetes diagnosis. The possibility of conducting an analysis separately for cancer type or considering specific cancer types based on the number of observed events will be evaluated. The same models will be used to estimate the association with the risk of recurrence, second cancer, or both in patients who have developed cancer. In this case, time to event will be calculated considering the difference in years between recurrence onset, second cancer, or last visit and the onset of the first cancer.

Linear regression models will be used to evaluate the relationship between variables measured at diagnosis and time to cancer onset. In case the assumptions of the linear model are not met (normality of residuals and homoscedasticity), the Spearman correlation coefficient will be calculated to measure the correlation between numerical variables and time to tumor onset, while the Mann-Whitney or Kruskall-Wallis tests will be used when variables measured at baseline are categorical.

The significance level will be set at 0.05, and all tests performed will be two-tailed. Finally, the analyses will be conducted using SAS software (version 9.4; SAS Institute, Cary, NC, USA).

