4. EXPECTED RESULTS

Through this research, we aim to obtain new information about the study population in order to better understand the possible correlation between the two pathologies. This will enable us to identify risk factors associated with metabolic pathology that may influence the development time of cancer, as well as to identify those that may contribute to carcinogenesis itself.

This knowledge will allow us to define the role of hyperglycemia, obesity, and other risk factors or behaviors in the context of cancers in order to act with appropriate prevention strategies, considering cancer as one of the possible complications of T2D.

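### Secondary objective 3 tests time to cancer onset with methods that ignore censoring, so it can report false associations and has little power for true risk factors

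*Combined protocol and SAP*

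**What the plan says.** Section 2 lists as the third secondary objective "Investigating the correlation between patient characteristics and time to cancer onset". Section 3.9 assigns it this method: "Linear regression models will be used to evaluate the relationship between variables measured at diagnosis and time to cancer onset". It then adds: "In case the assumptions of the linear model are not met (normality of residuals and homoscedasticity), the Spearman correlation coefficient will be calculated" for numerical variables, with Mann-Whitney or Kruskal-Wallis tests for categorical ones. All tests are two-sided at 0.05.

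The same section gives cancer-free patients a time that ends at their last visit, but it ties that rule to the Cox analysis and does not extend it to the linear models. No other section deals with censoring for objective 3.

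Two design features bear on this. Section 3.3 enrols patients seen "for a first diagnosis of T2D between 1990 and 2010". Section 3.6 says: "Patients included in the study will be followed from the date of diagnosis of T2D until the date of the last available visit". Section 4 expects the study to "identify risk factors associated with metabolic pathology that may influence the development time of cancer", as a result distinct from finding factors that cause cancer.

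**The concern.** A patient without cancer has no onset time. The linear and rank analyses must therefore either use cancer cases only, which is the natural reading, or enter last-visit times as if they were onset times. Both ignore censoring.

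Among cases, the observed onset time is limited by how long the patient could be observed. A patient diagnosed in 1990 can contribute an onset up to 20 years later after diagnosis than a patient diagnosed in 2010 can. Loss and death shorten the window further. A factor associated with year of diagnosis or with retention is then associated with case-only onset time, whatever it does to cancer. Conversely, a factor that raises the cancer rate yields more cases but barely changes when they occur.

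At stake is the Section 4 conclusion on what influences the timing of cancer. It could reflect who was followed longer, and it could contradict the study's own Cox results.

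**Working it through.** **The plan's own figure.** Objective 3 has no sample-size figure. Section 3.8 gives one for the Cox analysis: "it will be necessary to identify 779 cancer cases to highlight a Hazard ratio of 1.2". With two-sided alpha 0.05, 80% power, prevalence p = 0.13 and covariate correlation 0.1 (R² = 0.01), Schoenfeld's formula is

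events = (1.960 + 0.842)² / [p(1−p)(ln HR)²(1−R²)] = 7.849 / (0.1131 × 0.03324 × 0.99) = 2,109.

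The 779 is not reproduced. It is matched by ln HR = 0.3 (HR 1.35): 7.849 / (0.1131 × 0.09 × 0.99) = 778.9. That is a separate matter, and nothing below depends on it. It is the reason for showing power at both HR 1.2 and HR 1.35.

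**Inputs.** From the documents: diagnosis 1990–2010, follow-up to the last visit, two-sided 5% tests, 13% prevalence, HR 1.2. Assumed, because the documents give no values: even spread of diagnosis year, data closed in 2024, constant cancer hazard λ = 1.5% a year, loss or death μ = 4% a year, 4,000 patients (about 720–815 cancers).

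**Why case-only means mislead.** With constant hazards and maximum follow-up C years, onset times among cases have mean

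m(θ, C) = 1/θ − C/(e^{θC} − 1), where θ = λ + μ.

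Cancer hazard and loss enter only through their sum, so the case-only mean cannot tell them apart.

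- Diagnosis in 2010 (C = 14), θ = 0.055: 18.18 − 12.07 = 6.1 years.
- Diagnosis in 1990 (C = 34), θ = 0.055: 18.18 − 6.20 = 12.0 years.
- Mid-window (C = 24), θ = 0.055: 18.18 − 8.75 = 9.43 years.
- True HR 1.2 (λ = 0.018, θ = 0.058, C = 24): 17.24 − 7.94 = 9.30, a shift of −0.13 years.
- No cancer effect but loss of 6% (θ = 0.075, C = 24): 13.33 − 4.75 = 8.58, a shift of −0.85 years.

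A pure follow-up difference thus moves the mean more than six times as far as the effect the plan wants to detect (0.85/0.13).

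**Simulated rejection with no true effect** (2,000 replicates, nominal 5%; Mann-Whitney under differential loss comes from separate 1,000-replicate and confirmatory runs):

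| Factor | Linear | Mann-Whitney | Linear + year |
|---|---|---|---|
| Prevalence 20→80% over 1990–2010 | 60% | 41% | 5% |
| Prevalence 35→65% | 19% | 13% | 5% |
| Prevalence 10→16% | 5.5% | 6% | 5% |
| Loss 6% v 4% a year, prevalence 13% | 21% | 22% | 20% |
| Same, prevalence 30% | 37% | 37% | 35% |
| Same, prevalence 50% | 46% | 39–44% | 44% |
| Unrelated to follow-up | 5% | – | – |

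Full-cohort Cox and Weibull models, both adjusted for year, reject in 4–5% of replicates in every null scenario. Adjusting the linear model for year removes the calendar bias but not the loss bias. Section 3.9 names no such covariate.

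**Power at 13% prevalence.** HR 1.2: case-only linear 5.5%, Cox 46% (41% by Schoenfeld's formula), Weibull 45%. HR 1.35: 7% against 85%.

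**Fallback.** Shapiro-Wilk rejected normality of the case-only residuals in every replicate, so the unadjusted rank tests would probably be the ones reported. Section 3.9 names that test only for descriptive data, so applying it to residuals is an assumption.

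**Sensitivity.** With a cancer hazard that rises over time (Weibull shape 1.5), linear rejects 81% (20→80%) and 30% (35→65%), Mann-Whitney 72% and 25%. Under differential loss, linear rejects 19% and 42% at 13% and 50% prevalence. Year-adjusted Cox stays at 5–6%. A second simulation used about 779 events, hazards of 0.5–1.5% a year and loss only in its follow-up scenario:

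- Prevalence 15→11%: linear 5.9–7.4%.
- Prevalence 18→8%: linear 10–14%, Mann-Whitney 9–12%.
- Mean time to loss 10 v 20 years: linear 69–73%, Mann-Whitney 68–72%.
- Power at HR 1.2: linear 4.6–5.6%, Cox 42–44%.

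**The case against.** **The power comparison sets two different quantities side by side.** Cox estimates the rate of cancer in everyone; a case-only regression describes when cancer occurred in those who got it. Under a constant hazard ratio the second should hardly move, and the primary Cox analysis already searches for risk factors. This is right: the study as a whole loses no power for risk factors. It does not rescue the analysis, because Section 4 reads the result as influence on the development time of cancer, and a null result here would be misread as no influence.

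**The large error rates need inputs the documents do not give.** This also stands. At the only documented prevalence, 13%, a mild calendar trend (10→16%, or 15→11%) gives about 5.5–7%, and 18→8% gives roughly 8–14%. A loss difference of 5% against 4% a year gives 9–11%. The figures above 40% need a common factor with a strong trend, or markedly different follow-up.

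**The rank tests, not the linear model, would usually be reported.** For calendar trends their error rates are generally lower, though still 13–41% in the two stronger cases above. For differential loss they are about the same as the linear model's.

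**Year adjustment of Cox is not shown to be necessary.** Cox without year also stayed at about 4–7% in the null scenarios. The Weibull model was tried only on exponential or Weibull data, so its good behaviour is partly built in.

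None of this supplies a way of handling censoring for objective 3.

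**Conclusion.** The concern holds. The planned tests for objective 3 have no censoring term in a cohort whose possible follow-up differs by up to 20 years. They can therefore declare associations for factors linked to diagnosis year or retention, and they say almost nothing about factors that truly raise cancer risk. The direction follows from the design; the size depends on assumed hazards, loss, trends and data cut. Inflation ranges from negligible (weak trends, or factors unrelated to follow-up) to several times the nominal 5%.

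The damage is limited to one secondary objective and the related statement in Section 4. The primary analysis and the recurrence and second-cancer analyses already use Cox models. This should be fixed before analysis, but it does not threaten the primary result.

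**What to change.** In Section 3.9, replace the inferential linear, Spearman, Mann-Whitney and Kruskal-Wallis tests for objective 3 with a censoring-aware model on the whole cohort. Use the Cox model already planned, or a Weibull accelerated failure-time model, with its fit checked, if a time-ratio reading is wanted. Restrict the covariates to those measured at diagnosis. Adjust for year of diagnosis as a precaution; the date is already collected ("Date of diagnosis of T2D", Section 3.7). Report onset times among cases descriptively only, with a statement that they depend on length of follow-up. Adding year to the linear model alone is not enough, because bias from differential loss remains.

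The cost is a change of wording and a little more analysis, with no new data. The drawback is that a Cox version of objective 3 would largely overlap the primary analysis; the Weibull model keeps a distinct time-ratio result.

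### Objective 3: neither the linear model nor its rank-test fallback commits to adjusting for age or diagnosis year, and the trigger between them is undefined

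*Combined protocol and SAP*

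**What the plan says.** Section 2 lists as the third secondary objective: "Investigating the correlation between patient characteristics and time to cancer onset". Section 3.9 gives the method: "Linear regression models will be used to evaluate the relationship between variables measured at diagnosis and time to cancer onset". It names no covariates and does not say whether these models hold one variable or several. The terms univariate and multivariate are used in that section for the Cox models only.

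The fallback follows: "In case the assumptions of the linear model are not met (normality of residuals and homoscedasticity), the Spearman correlation coefficient will be calculated" for numerical variables, while "the Mann-Whitney or Kruskall-Wallis tests will be used when variables measured at baseline are categorical". No partial or stratified version, transformation or robust standard error is offered.

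No test or threshold is given for judging the residuals. The one normality check that section 3.9 names belongs to the descriptive statistics, where the median replaces the mean "if not distributed according to a normal random variable according to the Shapiro-Wilk test and observation of the QQ plot".

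Three facts elsewhere bear on this. Section 3.7 collects age, gender and the date of T2D diagnosis. Section 3.6 records cancer onset by calendar year and counts the interval in years. Section 3.3 takes patients seen "for a first diagnosis of T2D between 1990 and 2010 will be included in the study", so the longest observable interval depends on the year of diagnosis.

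**The concern.** The time from diabetes diagnosis to cancer plausibly depends on age at diagnosis, and the length of observation depends on both age and diagnosis year. A baseline characteristic that varies with age can then correlate with time to onset without influencing it. Section 4 hopes to identify factors that may affect how fast cancer develops and to use them for prevention, so a correlation produced by age could be read as a finding.

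Age is available, but section 3.9 does not promise to use it in the linear models, and once the fallback applies it cannot be used. The fallback is set off by features of the residuals that, with several hundred cases, mainly concern standard errors and can be handled without leaving regression. Because the trigger is undefined, the choice between branches would also be made after seeing the data.

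**Working it through.** **Figure in the documents.** Objective 3 has no sample size of its own. The only case count is the 779 in section 3.8, given for the Cox analysis at a hazard ratio of 1.2. It does not reproduce with the usual formula, events = (z_α + z_β)² / [p(1-p)(ln HR)²(1-R²)]. With two-sided 0.05, 80% power, p = 0.13 and R² = 0.1² = 0.01 this is (1.960 + 0.842)² / [0.13 × 0.87 × 0.1823² × 0.99], or 2,109 events. That is a separate matter; 779 serves here only as the number of cases.

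**Assumptions, none from the documents.** Age at diagnosis 62 (SD 11); Gompertz hazards for cancer and death; loss to follow-up 0-8% per year; data cut at the end of 2023. Diagnosis falls in 1990-2010, onset is in whole years, and only cases are analysed. The risk factor has no effect on cancer and has correlation rho with age. For Mann-Whitney, 13% are exposed. There were 300-600 runs per setting, with tests at two-sided 0.05.

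**Step 1: does the trigger fire?** Suppose it means Shapiro-Wilk or Breusch-Pagan p < 0.05 on the residuals.

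| Cases | One-variable model | Age-adjusted model |
|---|---|---|
| 100 | 96-100% | 79-99% |
| 200 | 100% | at least 99.5% |
| 400 and 779 | 100% | 100% |

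Under a judgement from plots the rate cannot be computed.

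**Step 2: false-positive rate for the null factor, 779 cases.** In this base case the correlation of age with time is about -0.37.

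| rho with age | Spearman | Mann-Whitney | Linear, unadjusted | Linear with age, robust SE |
|---|---|---|---|---|
| 0 | 6% | 4% | 7% | 6% |
| -0.1 | 17% | 10% | 20% | 6% |
| -0.2 | 44% | 21% | 48% | 5% |
| -0.3 | 84% | 42% | 87% | 4% |

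The age-adjusted linear model with ordinary standard errors gave 4-6% in the same runs, although the residual checks failed in all of them.

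**Step 3: hand check.** The correlation of the null factor with time is close to the product of its two links through age: at rho = -0.2, (-0.2) × (-0.371) = 0.074, against 0.067 in the simulation. For an induced correlation r, the rejection rate is about Φ(r√(n-3) - 1.96) + Φ(-r√(n-3) - 1.96). With r = 0.067 and n = 779, r√776 = 1.87, which gives 46% (simulated 44%). With r = 0.103 it is 2.87, which gives 82% (simulated 84%).

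**Step 4: sensitivity at rho = -0.2.**

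| Setting | Spearman | Linear with age, robust SE |
|---|---|---|
| 779 cases, no loss | 53% | 3% |
| 779 cases, 8% loss per year | 39% | 6% |
| 300 cases | 24% | 5% |
| 779 cases, age acts through death only | 16% | 5% |
| 779 cases, weak age-time relation (about -0.06) | 5% | 2% |
| 300 cases, weak age-time relation (about -0.07) | 7% | 7% |

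A separately built simulation at 779 cases, with its own assumed hazards, also fired the switch in 100% of runs. It gave Spearman rates of 3-6% at rho = 0 and 55-77% at rho = -0.3, unadjusted linear regression 30-52% at rho = -0.2, and a linear model with age, diagnosis year and HC3 errors 3-8%. Taking both together, Spearman runs from 3-6% to 55-84% and Mann-Whitney from 4-6% to 24-42%.

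**The case against.** A reader might infer that the switch itself throws away an adjustment the plan would otherwise make. The documents do not support that. The linear models are never said to be multivariable, and a fallback with one test per variable reads naturally as the counterpart of one-variable regressions. Unadjusted linear regression is inflated about as much as Spearman (48% against 44% at rho = -0.2), so deleting the switch alone would change almost nothing. This objection stands, and it moves the defect to the missing commitment to age in both branches.

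A reader might also infer that the rule is bound to fire. That holds only under formal tests; section 3.9 names none for residuals, and a reading of plots could go either way.

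Nor does every age-related variable produce a spurious result. At rho = -0.1 Spearman rejects in 17% of runs, and with a weak age-time relation there is no material inflation. The documents give neither correlation.

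Finally, the objective is secondary and worded as a correlation, which a marginal rank coefficient answers literally. The primary objective has its own multivariable Cox model. That limits the scope but does not close the gap: stepwise selection does not guarantee that age stays in the Cox model, and section 4 expects more from time to onset than a description.

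**Conclusion.** The point holds in limited form. For objective 3 neither branch commits to adjusting for age or diagnosis year, the fallback as written excludes adjustment, and the trigger is undefined. These three statements rest on the text alone.

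The size is conditional on ages, hazards and correlations that the documents do not give. At 779 cases the false-positive rate of the rank methods ranges from nominal, when the factor is unrelated to age or age is only weakly related to time, to 55-84% (Spearman) and 24-42% (Mann-Whitney) at a factor-age correlation of -0.3. Including age (and diagnosis year) with robust standard errors holds it at about 3-8% over the same range of correlations. The change should be made before analysis, but it concerns a secondary objective and does not touch the primary Cox analysis.

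**What to change.** In section 3.9, replace the switch with one multivariable model for objective 3 in which age at diagnosis, sex and diagnosis year are always included. Use HC3 or bootstrap standard errors whatever the residual checks show. Report Spearman coefficients and the Mann-Whitney and Kruskal-Wallis comparisons as description only. Forcing in age and diagnosis year is the active part of this change.

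The cost is a sentence or two of text. The covariates are already collected under section 3.7, and robust standard errors are a standard option.

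This does not resolve the separate problem that an analysis restricted to cases ignores the follow-up of patients without cancer. If objective 3 is moved to a time-to-event model for that reason, the fallback disappears and the same covariates should be forced in there.
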